		1.1. Revision Date(s) add rows as needed

2. Background

Briefly discuss the important literature relevant to the trial and that provides background for the trial. Include the importance of the trial and any relevant treatment issues or controversies.

Bone grafting following tooth extraction is often performed to preserve bony ridge dimensions adequate to support subsequent implant placement. Alveolar ridge resorption commonly occurs following tooth extraction, and the decrease in bone volume has the potential to make dental implant therapy impossible without surgery to reconstruct the ridge. The aim of ridge preservation grafting is to prevent or minimize this resorative process, thereby preserving an adequate volume of bone for implant placement. Ridge preservation generally involves placement of a particulate bone graft material in the tooth socket, followed by use of a membrane or similar substance over the socket entrance to contain the bone graft.

Various grafting materials have been recommended for these ridge preservation procedures, including cortical and cancellous freeze-dried bone allograft (FDBA), demineralized freeze-dried bone allograft (DFDBA), various xenografts, alloplasts and autografts. Our research group here in the Department of Periodontics at the UT Health Science Center at San Antonio has spent several years evaluating wound healing and clinical changes in ridge dimension following ridge preservation procedures using a variety of bone grafting materials and treatment protocols.⁽¹⁻⁹⁾ In most of these studies, bone allografts were used for ridge preservation. For various reasons, many clinicians prefer not to use human bone graft products, recommending use of xenografts or alloplastic materials instead. Our study group has previously examined use of various bovine xenografts.⁽¹⁻¹⁰⁾

Of interest are two composite materials that include either bovine bone or hydroxyapatite granules and sugar cross-linked collagen. These materials possess better handling properties that allow them to be used without the addition of a membrane during ridge preservation procedures. Two such composite materials are currently available in the U.S - a composite bovine xenograft with porcine collagen matrix and a hydroxyapatite graft with porcine sugar cross-linked type I collagen tendon matrix. The bovine/collagen matrix has been extensively researched for ridge preservation procedures.⁽¹¹⁻¹⁷⁾

The porcine collagen in the newer hydroxyapatite-containing composite graft material is cross linked with sugar with a proprietary technology (Glymatrix®). This cross-linking technology has shown promising results in its use as a membrane.^(3, 18, 19)

However, only a recent animal study presented as a poster at the 2017 Academy of Osseointegration on beagle dogs compared the two composite materials for a ridge restoration procedure.⁽²⁰⁾ The results of this animal study showed comparable healing and biocompatibility profiles, increased percentage of vital bone and a larger overall ridge restoration for the hydroxyapatite/collagen matrix.

3. Objectives and Endpoints *All data points collected in the study should support an objective or have a regulatory purpose.* *Complete the table – add rows as needed.*

3.1. Objective(s) Clearly and concisely define the primary and secondary outcomes.	3.2. Endpoint Clearly define the endpoints. (endpoints are the basis for concluding that the objective has been met.)	3.3. Justification for Endpoint Briefly explain why the endpoint(s) were chosen.
Is there a difference in histologic wound healing following tooth extraction and ridge preservation between groups treated with Bio-Oss® Collagen compared to Ossix™ Bone	% vital bone formation, % residual graft material, and % "CT/other" (fibrous tissue and marrow space)	% vital bone formation shows the amount of new bone formed after the procedure. The higher this % is the better the healing of the site % residual graft material shows how much of the graft material remained intact. Ideally all the graft materials should turn over to vital bone

		% CT/other (fibrous tissue and marrow space) is the amount of tissue that is neither native bone or graft material. It may be connective tissue that will mature to osteoid and bone or marrow space that is part of the normal healing.
	Change in ridge width; Change in buccal ridge height, and Change in lingual ridge height	

4. Rationale

Briefly state the reason for conducting the clinical trial.

A recent animal study presented as a poster at the 2017 Academy of Osseointegration on beagle dogs compared the two composite materials for a ridge restoration procedure. (20) The results of this animal study showed comparable healing and biocompatibility profiles, increased percentage of vital bone and a larger overall ridge restoration for the hydroxyapatite/collagen matrix. The proposed study will assess the histologic healing of this material in humans and compare it to a similar material that is well researched.

5. Study Design

5.1. Number of Groups/Arms		2	Group name(s)	Active control group – Bic-Css® Collagen Test group – Ossix™ Bone			
5.2. Overall Design Select all applicable							
	Randomization		Cluster Randomized				
	Group-Sequential		Adaptive Design				
	Parallel Design		Placebo-Controlled				
	Superiority		Equivalence		Non-inferiority		
Device		Pilot		Pivotal		Post-Approval	
Drug/Biologic		Phase 1		Phase 1/2		Phase 2	
						Phase 2/3	
						Phase 3	
							Phase 4
	Dose escalation	If yes, details →					
	Dose ranging	If yes, details →					
	Sub-studies	If yes, details →					

5.3. Other Design Details:

6. Study Population

6.1. Study Population(s) Label/Name	6.2. Identify the criteria for inclusion The criteria that every potential participant must satisfy, to qualify for study entry.	6.3. Identify the criteria for exclusion The characteristics that make an individual ineligible for study participation.
To add more populations – select a row, copy & paste	All individuals in this study population must meet all of the inclusion criteria in order to be eligible to participate in the study	All individuals in this study population meeting any of the exclusion criteria at baseline will be excluded from study participation.
Dental patients needing extraction	
 One tooth, excluding molars, that has been identified by dental 	
 Will not cooperate with the follow-up schedule.

	
faculty as requiring a single tooth extraction
 
 • A dental implant is indicated and treatment planned to replace the missing tooth • Have adequate restorative space for a dental implant-retained restoration • Have at least 10mm of alveolar bone height, without impinging on the maxillary sinus or inferior alveolar canal. • Have a dehiscence of the buccal or lingual bony plate of the tooth socket extending no more than 50% of the total depth of the socket. • Female patients who have undergone a hysterectomy, tubal ligation, or menopause, and non-pregnant women of child-bearing potential. • Are nonsmokers or former smokers. Current smokers may be included if they smoke ≤ 10 cigarettes per day 	
 • Patients will not be entered who are mentally incompetent, prisoners, or pregnant. • Pregnant women or women intending to become pregnant during the study period (as confirmed verbally; an over the counter pregnancy test will be provided if pregnancy status is unknown or suspected). • Patients who become pregnant during the study will be withdrawn and standard care will be delivered. • Smokers who smoke >10 cigarettes per day • Clinical and/or radiographic determinations which will preclude inclusion in this study are: Active infection other than periodontitis; Inadequate bone dimensions or restorative space for a dental implant; Presence of a disease entity, condition or therapeutic regimen which decreases probability of soft tissue and bony healing, e.g., poorly controlled diabetes, chemotherapeutic and immunosuppressive agents, autoimmune diseases, history of bisphosphonate use or long-term steroid therapy; Positive medical history of endocarditis following oral or dental surgery.

6.4. Will screen failures be allowed to re-screen at a later date?
	
 No  Yes If yes, describe criteria below ↓
 
Subjects who do not meet inclusion criteria initially may be re-screened and included in the study if inclusion criteria is met at a later date
	

7. Study Intervention(s) being tested or evaluated

This can include prevention, diagnostic or therapeutic interventions (e.g., drug or device) or educational, health services or basic science interventions (e.g., educational program, health care delivery model, or examining basic physiology)

- 1) Active Control Group: Bio-Oss® Collagen, (Geistlich, Inc.), 90% bovine derived xenograft granules and 10% porcine collagen.
- 2) Test Group: Ossix™ Bone (Datum Dental Ltd), a resorbable sponge-like matrix of 80% hydroxyapatite and 20% sugar cross-linked porcine collagen.

8. Protocol-Directed procedures, items, services or tests

List all procedures directed by the study plan - including items or services provided as part of routine or conventional care and those needed to diagnosis or treat research related complications.

Important Note – The protocol directed procedures listed must match those in the [Schedule of Activities \(attachment\)](#)

8.1. Drugs (trade and generic, dosage, route of administration)

Either Amoxicillin 500mg three times per day for 7 days, or if they are allergic to penicillin/amoxicillin they will be prescribed Clindamycin 300mg three times per day for 7 days. Antibiotics will be used for an approved indication and are routinely prescribed as part of routine care.

8.2. Devices

Bio-Oss® Collagen and Ossix™ Bone are both classified as devices by the FDA. Both will be used for an approved indication (in accordance with approved labeling).

8.3. Biologics

N/A

8.4. Laboratory Tests

If needed: An over-the-counter urine pregnancy test will be provided to female subjects and self-administered in the graduate periodontics clinic of UTHSCSA. A negative result is required to enter the study.

Histology of the core bone biopsy

8.5. Imaging Procedures**8.6. Other Research Procedures (e.g., other safety and efficacy assessments.)**

1) Impressions of the arch with tooth to be extracted; 2) fabrication of a ridge measurement stent; 3) tooth extraction & ridge preservation; 4) dental implant placement & core bone biopsy; 6) bone quality determination (Lekholm and Zarb classification);

8.7 Attach a Schedule of Activities (SOA) Excel File [Download the Template here: [Schedule of Activities](#)]

Check to indicate that the SOA Excel File is attached →

8.8 Description of Methods (or include in separate document)

Check to indicate that the Methods are described in an attached file →

Each extraction socket will receive one 5 X 5 X 8mm or 5 X 5 X 10mm graft cube (research) with no attempt to fill the entire socket. No wound dressing or membrane will be used to cover the bone graft material as both materials can be used alone. All extraction sockets will be sutured with Vicryl 4.0 mattress suture which will be removed approximately 2 weeks (\pm 1 week) after the procedure as per standard of care. All patients will be prescribed an oral antibiotic after the procedure either Amoxicillin 500mg three times per day for 7 days, or if they are allergic to penicillin/amoxicillin they will be prescribed Clindamycin 300mg three times per day for 7 days as per standard of care.

In keeping with the protocol our study group has used several times before, the plan will be to extract non-molar teeth and graft with the test/control materials. Each subject will provide a single non-molar tooth site for study treatment. Following approx. 14 weeks of healing, we will harvest a core biopsy at the time of implant placement. The core biopsy will then be evaluated for the primary outcomes: % vital bone formation, % residual graft material, and % "CT/other" (fibrous tissue and marrow space). We will also evaluate the following secondary outcomes using a custom measuring stent for each subject: change in ridge width; change in buccal ridge height, and change in lingual ridge height. During the 14-week healing period, subjects will be followed up with biweekly and monthly visits as per standard of care, to evaluate healing.

A detailed visit by visit outline is provided below:

Step-by-Step Methods: All the procedures are routinely performed in the graduate periodontics clinic as part of standard care. The methodology is the same previous studies of our group HSC20130470H, HSC20150708H, HSC20170339H, HSC20170267H, among others.

Visit 1 - Screening examination:

If a patient presents at a consultation appointment at the graduate periodontics clinic with a non-molar tooth (incisors, canines, premolars) that needs to be extracted and replaced with a dental implant, the treating doctor will provide:

- Explanation to the patient of the purposes of the study and the planned procedures related to the study.
- Explanation to the patient of the risks, benefits and possible complications of participation in the study.
- Notification to the patient that inclusion in the study is voluntary and conditional upon satisfying the inclusion and exclusion criteria.

Patient will be given the opportunity during the appointment to ask any question that he/she may have. Following an informational discussion with the prospective subject, consent will be obtained within 2 weeks. This is up to the discretion of the patient. If the patient would like to become a subject for entry into the study, he or she can do so immediately, or can consider it for up to 2 weeks (must be prior to extraction).

Visit 2 – Extraction with ridge preservation using either 90% bovine derived xenograft granules and 10% porcine collagen (Bio-Oss® Collagen, Geistlich, Inc.) or a resorbable sponge-like matrix of 80% hydroxyapatite and 20% sugar ross-linked porcine collagen (Ossix™ Bone, Datum Dental Ltd).

The patient will be assigned to either group by simple randomization with a 1:1 ratio

If the patient has agreed to participate in the study, informed consent will be obtained and documented on a written consent form. If not, standard care treatment will be provided to the patient, but the patient would not be included in the study.

On the day of the planned extraction, the medical history will be updated.

Pregnant women or women intending to become pregnant during the study period: Prior to dental surgery, females of child-bearing age are asked verbally if there is any possibility that they are pregnant. If not, we proceed with surgery and no pregnancy test is done. If the woman states that there is a possibility that she is pregnant, an over the counter urine pregnancy test to rule pregnancy in or out will be provided. Use of the urine pregnancy test is only done if she says she may be pregnant. [If needed: Urine pregnancy test will be provided to female subjects in the graduate periodontics clinic of UTHSCSA and a negative result is required to enter the study.]

Impressions of the arch with the tooth to be extracted in place will be taken prior to extraction and poured in stone to obtain initial study casts (research). If the tooth to be extracted is fractured, a wax-up of the tooth will be made before the stent is fabricated (research).

One measurement stent will be fabricated to facilitate clinical ridge measurements. A clear suck-down resin measuring stent will be fabricated in the laboratory to allow standardization of the location of clinical measurements of ridge width and height through small holes that will be placed in the stent at the time of tooth extraction.

The width of keratinized tissue will be recorded clinically to the nearest 0.5mm using a periodontal probe at the mid-buccal and mid-lingual sites of the tooth to be extracted.

A pre-operative periapical radiographic image will be taken before the extraction as per standard of care (if not already available).

At the time of surgery, local anesthesia will be administered. Conscious sedation will be administered according to patient need and investigator preference, per standard care. Buccal and lingual flaps will be minimally reflected to a point up to 3mm apical to the bony crest.

Prior to tooth extraction, the clinical measuring stent will be placed and measurements of ridge width and ridge height will be taken and recorded to the nearest 0.5mm. Ridge width will be measured to the nearest 0.5mm using a ridge caliper at a point approximately 4mm apical to the facial and lingual bony crest through small holes created in the stent at those locations. Ridge height will be measured to the nearest 0.5mm through two holes in the occlusal aspect of the stent – one hole directly above the facial bony crest and another hole directly above the lingual bony crest. This stent will be retained for use during the subsequent implant placement surgery.

Tooth extraction will be performed as atraumatically as possible. Following tooth extraction, a final determination of enrollment into the study will be conducted based on the integrity of the buccal bone wall plate at the extraction site. If the buccal plate is intact, defined as no bony dehiscence greater than 50% of the socket depth, the patient will remain enrolled in the study.

Conversely, if the buccal plate integrity has not been maintained (bony dehiscence >50%) the patient will be exited from the study and standard care therapy will be delivered to the patient.

After extraction, the number of bony walls in each socket will be recorded along with the presence of any bony dehiscences or fenestrations. Buccal and lingual flap elevation will be minimized and will extend no more than 2-3mm beyond the bony crest on the facial and lingual surfaces. The buccal plate thickness will be measured using an Iwanson gauge positioned perpendicular to the inner wall of the extraction socket. One beak of the gauge will be placed within the extraction socket 1.0mm apical to the alveolar bone crest. The other beak will be placed on the external bone surface. This buccal plate thickness measurement will be recorded to the nearest 0.1 mm.

The socket will be thoroughly debrided, a 5 X 5 X 8 mm or 5 X 5 X 10 mm bone graft cube of either 90% bovine derived xenograft granules and 10% porcine collagen (Bio-Oss® Collagen, Geistlich, Inc.) or a resorbable sponge-like matrix of 80% hydroxyapatite and 20% sugar cross-linked porcine collagen (Ossix™ Bone, Datum Dental Ltd) will be soaked in patient's blood and inserted in the socket. No attempt will be made to completely fill the socket as the materials expand after they contact fluids. No membrane or wound barrier will be placed over the graft in either group. Vicryl 4.0 sutures will be placed over the graft material to secure it in place as part of standard of care. Primary closure will not be attempted.

Visit 3 - Post-operative visit

The post-operative visit after extraction/ridge preservation will be scheduled approximately 3 weeks (± 1 week) after the procedure. If needed, an optional POT visit may be scheduled before this visit, per standard care and as determined by patient need.

Visit 4 - Pre-implantation:

Approximately 3 months after the extraction (\pm 2 weeks) a CBCT of the prospective implant site may be taken as needed per standard care. The implant surgery will ensue within 2 weeks (\pm 2 weeks). The CBCT is not part of the study but rather standard of care.

Prior to surgery, pregnancy status will be confirmed verbally. An over the counter pregnancy test will be provided if pregnancy status is unknown or suspected (research). A negative result is required to continue being in the study.

Visit 5 - Implant placement:

Prior to surgery, pregnancy status will be confirmed verbally. An over the counter pregnancy test will be provided if pregnancy status is unknown or suspected (research). A negative result is required to continue being in the study.

Approximately 16 weeks (\pm 2 weeks) after the extraction, implant surgery will be performed (standard of care). The width of keratinized tissue will be measured at the prospective implant site. A piece of floss will be run over the keratinized tissue and cut to the width of keratinized tissue, i.e. from the mucogingival junction (MGJ) on the buccal to the MGJ on the lingual. The floss will be then measured with a ruler to the closest 0.5mm.

After local anesthesia (and conscious sedation if requested), the patient will undergo implant placement surgery at the previously extracted tooth site and if required simultaneous guided bone regeneration (GBR) will be performed as per standard care. First, the individual subject's measuring stent and caliper will be used to determine the ridge width and ridge height at the same locations as done in the tooth extraction/grafting surgery visit. During the implant bed preparation, a hollow drill will be used to allow retrieval of a bone core which will be collected and stored in formalin and subsequently examined histologically and outcomes including percentages of new bone formation, residual graft and connective tissue/other will be recorded.

- During the implant placement procedure, the following data will be recorded per standard care:
- Bone quality according Lekholm and Zarb (1985) classification
- Absence/Presence of bone defect, including dehiscence or crater like defect. If present, at what site(s) (Buccal, Mesial, Lingual, Distal) and what are the respective depth and width of these defects.
- Absence/Presence of bone fenestration. If present what is the size of the fenestration in height and width.
- Was additional bone grafting needed in case of thin bone or dehiscence of threads? Yes/No

Subject participation ends at the time of implant placement. However, standard care post-operative visits will be provided after implant placement. Generally, one or two post-operative visits will be provided during the first month after implant surgery to insure adequate healing.

9. Preparation/Handling/ Storage/Accountability of Investigational Drug, Biologic, or Device

N/A - This study does not include any investigational products (e.g. drugs, devices or biologics)

N/A - An Investigator Brochure is attached

N/A - A Drug/Device Manual is attached

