12.1. Statistical Hypotheses

State the formal and testable null and alternative hypotheses for primary and key secondary endpoints, specifying the type of comparison (e.g., superiority, equivalence or non-inferiority, dose response) and time period for which each endpoint will be analyzed.

Hypotheses: a.) No difference in % vital bone, % residual graft and % connective /other tissues between BioOss Collagen and Ossix Bone groups. b.) No dimensional differences in alveolar ridge after ridge preservation with BioOss Collagen or Ossix Bone.

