12.2. Sample Size Determination

Include number of participants to recruit, screen, and enroll to have adequate power to test the key hypotheses for the study. Provide all information needed to validate your calculations and judge the feasibility of enrolling and following the necessary number of participants.

Power analysis revealed a sample size of 14 patients per group was enough to detect a mean difference in percentage of new bone formation of 1 SD by Mann-Whitney U test at the 0.05 level with a power of 88.5%. Anticipating a potential 30% dropout rate and needing 14 fully compliant patient per treatment group, 22 patients will be enrolled in each group.

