12.4. Statistical Analyses

Include analysis of primary efficacy endpoints, secondary endpoints, safety analyses, and any planned interim analyses

The outcomes of the histologic and clinical parameters will be summarized with the sample size, mean, standard deviation, median, minimum and maximum. The significance of variation in the mean with group BioOss collagen or Ossix Bone will be assessed with two-sample *t*-testing. The significance of variation in the group effect with another variable will be assessed with an interaction term in a linear model. All statistical testing will be two-sided with a significance level of 5%. Spearman rank and Pearson correlations between clinical parameters and histologic parameters will be analyzed as well. All statistical analyses will be done with statistical software.

References:

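### Three co-primary tissue percentages share one null hypothesis, each tested at 5%, and no rule says which result rejects it; the trial is sized on new bone formation alone

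*Combined protocol and SAP*

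**What the plan says.** - **Section 3** sets one histologic objective with three endpoints: % vital bone, % residual graft and % CT/other. The form's own guidance there is that "endpoints are the basis for concluding that the objective has been met". Residual graft has a separate rationale ("Ideally all the graft materials should turn over to vital bone"), and CT/other "is the amount of tissue that is neither native bone or graft material".
- **Section 8.8** gives all three primary status: "The core biopsy will then be evaluated for the primary outcomes: % vital bone formation, % residual graft material", followed by CT/other.
- **Section 12.1** states hypothesis (a) as a single sentence: "No difference in % vital bone, % residual graft and % connective /other tissues between BioOss Collagen and Ossix Bone groups".
- **Section 12.2** considers one of the three: "Power analysis revealed a sample size of 14 patients per group was enough to detect a mean difference in percentage of new bone formation".
- **Section 12.4** says that the group difference in means "will be assessed with two-sample *t*-testing" and that "All statistical testing will be two-sided with a significance level of 5" percent. It gives no order of testing, no adjustment, and no statement that any one or all of the three must be significant.

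**The concern.** The plan has one objective and one null hypothesis but three tests, and nothing links the tests to the hypothesis. Three rules are open: any one significant result rejects (a), all three must be significant, or each percentage is a separate question. They carry different error rates, and with none declared the choice can be made after the data are seen.

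The awkward case is a trial in which residual graft or CT/other reaches p<0.05 and vital bone, the only outcome used for sizing, does not. The plan does not say whether that trial has shown a histologic difference.

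**Working it through.** **Inputs from the documents.** Three primary outcomes (8.8), one null (12.1), two-sample t-tests two-sided at 0.05 (12.4), 14 completers and 22 enrolled per group, and a 1 SD difference in new bone (12.2).

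**Assumed inputs.** The documents give no SDs or correlations. I take normal data, a residual graft SD (s) of 0.2 to 2 times the vital bone SD, a vital bone-graft correlation (r) of -0.95 to +0.95, and percentages that sum to 100%.

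**Step 1: the plan's own figure.** Section 12.2 states 88.5% power at 14 per group by Mann-Whitney for 1 SD. For a t-test the noncentrality is 1 × √(14/2) = 2.646 with 26 df and critical value 2.056, which gives 72%. Simulated Mann-Whitney power with normal data is 68-70%. The stated figure does not reproduce at 14 per group; two-sided Mann-Whitney gives 88.4-88.5% at 22. This is a separate issue. It matters here only because the power figures in Step 5 are recomputed and are not the plan's.

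**Step 2: independent reference.** If the three outcomes were independent, P(at least one p<0.05) = 1 - 0.95³ = 0.143 (14.2% by simulation).

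**Step 3: with the dependence.** If CT/other = 100 - vital bone - graft, only two components are free. With vital bone SD 1, the CT/other SD is √(1 + s² + 2rs). I simulated null trials with three two-sided t-tests at 0.05:

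| Graft SD / vital bone SD (s) | r | Any one p<0.05, n=14 / n=22 | All three p<0.05, n=14 / n=22 |
|---|---|---|---|
| 1 | -0.5 (all SDs equal) | 12.3% / 12.2% | 0.0% / 0.0% |
| 1 | 0 | 11.7% / 11.8% | 0.1% / 0.1% |
| 0.5 | -0.5 | 11.5% / 11.4% | 0.1% / 0.1% |
| 0.5 | +0.5 | 9.9% / 9.7% | 0.9% / 0.9% |
| 1 | +0.8 | 8.0% / 8.0% | 2.1% / 2.2% |
| 1 | +0.95 | 6.5% / 6.5% | 3.5% / 3.5% |

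The SD ratio also matters. At s = 0.2 the any-one rate is about 8.6% at r = -0.8 and about 6.9% at r = -0.95, so no single figure per correlation holds over the whole SD range. Over the full range the any-one rate runs from about 6% to about 12%. It nears 5% only as the outcomes become almost perfectly correlated (5.6% at s = 1, r = +0.99).

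**Step 4: the discordant result.** P(graft or CT/other significant, vital bone not) = P(any one) - P(vital bone) = P(any one) - 5%. Simulated low and high values of about 6.5% and 12.5% give 1.5% and 7.5% of null trials.

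**Step 5: what adjustment would cost.** Holm's first threshold is 0.05/3 = 0.0167, and power at that level is a lower bound on Holm power. For a 1 SD vital bone difference by t-test:

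| Per group | Power at 0.05 | Power at 0.0167 |
|---|---|---|
| 14 | 72% | 54% |
| 22 | 90% | 79% |

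**The case against.** The strongest objection is that the plan never says one significant p-value rejects (a). Section 12.4 is compatible with three comparisons reported side by side, each at its own 5%. If all three had to be significant, the error rate would fall below 5%. This stands. A reader might infer that the trial runs at 12% or 14% type I error. The documents do not support that: inflation follows only under the any-one rule, and 14% also needs independence, which percentages of the same biopsy core would not have if they sum to 100%. What does not fall away is the missing rule, since Sections 3 and 12.1 frame one objective and one hypothesis.

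A second objection is that the sum to 100% is inferred. This also stands: Section 3 defines CT/other against native bone, not vital bone, so the 6-12% must carry that assumption.

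A third is that making vital bone the sole primary outcome is a reviewer's preference. In part it is. A reader might infer from Section 12.2 that the investigators already treat the other two as secondary. Sizing on one outcome does not show that, and Section 3 gives residual graft its own rationale. The choice is theirs, but it should be written down before analysis.

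**Conclusion.** The concern holds as a missing decision rule. Sections 3, 8.8, 12.1 and 12.4 together do not define what result rejects (a), and no other section supplies it. The consequence depends on the rule:

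- **Any one p<0.05 rejects (a):** about 6-12% false positives under the assumptions listed above, and about 14% if the three were independent. Every setting tried exceeded 5%, so the direction does not depend on the assumed SDs and correlations; the size does.
- **All three required:** 0 to about 4%.
- **Three separate nulls:** 5% each, with no statement of which one answers the objective.

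The vital bone comparison taken alone is a valid 5% test, and nothing here says otherwise. The mismatch between the stated 88.5% and recomputed power neither supports nor weakens this point.

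**What to change.** In Sections 3, 8.8, 12.1 and 12.4, name % vital bone, the outcome the trial was sized on, as the single primary outcome, tested two-sided at 5%, and restrict hypothesis (a) to it. Make % residual graft and % CT/other secondary. Report each as a between-group difference with a 95% confidence interval, and state that neither alone rejects (a).

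**Cost.** This is a text change in four sections. The vital bone test, its level and the sample size are unchanged. The real price is a narrower primary objective: residual graft and CT/other can no longer support a primary claim on their own.

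**If all three stay primary.** Use Holm across the three tests, which is valid whether or not the percentages sum to 100%, and restate the power. For a 1 SD vital bone difference it is at least 54% at 14 per group and 79% at 22, against 72% and 90% unadjusted. These are recomputed t-test values, so the restated section should not set them beside the 88.5% Mann-Whitney figure without explanation.
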